### **8.3.2.4 T Cell Receptor Excision Circles (TREC) in the Peripheral Blood**

TREC levels on T cells and mononuclear cells will be summarised for each group of IMP treated subjects at each visit using descriptive statistics. Plots of the median and range over time on a logarithmic scale will be produced. In addition, individual subject plots of TREC levels over time will be produced.

## **8.3.3 Additional Efficacy Endpoints**

### **8.3.3.1 Use of PEG-ADA Enzyme Replacement Therapy**

The time to withdrawal of PEG-ADA ERT will be calculated (in months) as:

$12 * (\text{stop date of PEG-ADA ERT} - \text{date of transplant}) / 365.25$ ,

or, for HSCT control subjects for whom the dates were not recorded, as:

age in months when PEG-ADA stopped – age in months at transplant.

Time to withdrawal of PEG-ADA ERT will be summarised for each of the IMP treated and HSCT control groups using descriptive statistics and, if appropriate, estimated from a Kaplan-Meier curve in which subjects who are still receiving PEG-ADA ERT will be censored at the time of their last visit.

### **8.3.3.2 T Cell V $\beta$ Panel**

Results of the T cell V $\beta$  panel spectratyping will be reported as normal or abnormal. The number (%) of subjects with normal/abnormal results will be summarized by visit for each of the IMP treated groups along with the number (%) with an abnormal result at any post-infusion visit.

### **8.3.3.3 PHA Stimulation**

PHA stimulation results will be categorised as normal proliferation, impaired proliferation, absence of proliferation or other. The number (%) of subjects falling into each category will be summarized by visit for each of the IMP treated groups.

The PHA stimulation index will be calculated as the stimulated PHA/unstimulated PHA and will be summarized at each visit for each of the IMP treated groups. In addition, the median and range will be plotted over time on a logarithmic scale.

### **8.3.3.4 CD3 Stimulation**

CD3 stimulation results will be reported as normal or abnormal. The number (%) of subjects with normal/abnormal results will be summarized by visit for each of the IMP treated groups along with the number (%) with an abnormal result at any post-infusion visit.

### **8.3.3.5 Vector Integration Analysis**

The number (%) of subjects with one integration site representing > 30% of total integration will be summarized by visit for each of the IMP treated groups. The number (%) of subjects for whom one integration site contributed > 30% of total integration at 2 or more time points will be summarized for each of the IMP treated groups. In addition, the total number of integration sites will be summarized by visit for each of the IMP treated groups.

### **8.3.3.6 Bone Marrow Aspirate**

A bone marrow aspirate may be performed for vector copy number, qPCR and integration analysis. Morphology and integration analysis results will be reported as normal or abnormal. The number (%) of subjects with normal/abnormal results for each of the tests will be summarized by visit for each of the IMP treated groups. In addition, the vector copy number in BM-MNC will be summarised using descriptive statistics.

### **8.3.3.7 Response to Tetanus Vaccination**

The response to the tetanus vaccination will be reported as normal or abnormal. The number (%) of subjects with normal/abnormal results will be summarised for each of the IMP treated groups.

## **8.3.4 Sensitivity Analyses**

Protocol violations in this study will be reviewed prior to database lock in order to determine whether any major violations have occurred that could have influenced the outcome of the study. In the event that such violations have occurred, sensitivity analyses will be carried out in order to assess the impact of these violations on the efficacy results.

Sensitivity analyses will be carried out for:

- Overall and event free survival (descriptive statistics and Kaplan-Meier analyses)
- Lymphocyte subsets (descriptive statistics and plots)

- Measures of engraftment (descriptive statistics and plots)

## 8.4 Safety Analyses

### 8.4.1 Adverse Events

All adverse events will be coded using MedDRA version 20.0 or higher

#### 8.4.1.1 Definition of Treatment-emergent Adverse Events

Adverse events (AEs) will be summarised on the basis of treatment emergence. An adverse event is considered to be treatment emergent if it occurred on or after the date and time of the start of the IMP infusion. If the start time of the event is not present, any event starting on the same day as the infusion will be considered to be treatment emergent. If the start date of the adverse event is partial or missing, it will be considered to be treatment emergent if:

- the day is missing, the month and year are present and are the same as or after the month and year of the infusion and the end date is missing or is not before the date of infusion,
- the day and month are missing, the year is present and is the same as or after the year of the infusion and the end date is missing or is not before the date of infusion,
- the entire date is missing and the end date is missing or is not before the date of infusion.

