#### **Safety**

Safety will be analysed descriptively by arm and study phase using the safety analysis population. Coding will be done using MedDRA version 18.1 or higher. The safety of treatment will be summarised using AEs, laboratory assessments and clinical examination assessments. These will be analysed continuously from pre-gene therapy to study completion, depending on the data available. Further details are given in the SAP.

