### 4.2 Secondary Objectives

The secondary objectives are to:

- Compare overall survival and event-free survival at 2 and 3 years between patients treated with IMP and patients treated with allogeneic HSCT
- Determine the percentage of IMP treated patients requiring immunoglobulin replacement therapy at all evaluation points from 18 months onwards
- Compare frequency of infections, and growth of pathogenic microorganisms over 3 years
- Evaluate the longitudinal clinical effect in terms of improved immunity
- Evaluate tolerability of conditioning regimen. These data will be reviewed and interpreted by the PI and the study team
- Evaluate feasibility of the transduction procedure. These data will be reviewed and interpreted by the PI and the study team.

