#### 8.4.1.2 Adverse Events

Treatment emergent adverse events will be summarised for each of the IMP treated groups in an overall summary presenting the number (%) of subjects with:

- any AE,
- moderate or severe AE,
- severe AE,
- treatment related AE (possibly/probably/definitely/not assessable/missing),
- AE leading to study withdrawal,
- any serious adverse event (SAE),
- treatment related SAE,
- SAE leading to death.

Incidence and frequency of treatment emergent AEs will be summarised for each of the IMP treated groups by system organ class (SOC) and preferred term (PT):

- overall,
- by maximum severity,
- by maximum relationship to treatment,
- treatment related AEs,
- AEs leading to study withdrawal (if sufficient events).

In addition, a summary table for the most frequently reported treatment emergent adverse events (those reported in 2 or more subjects) will be presented by PT in descending order of incidence and frequency.

In each table, if the same SOC or PT is reported on multiple occasions for a single subject, it will only be included once in the summary. In the table by maximum severity, only the most severe occurrence for each SOC and PT for each subject will be included in the summary. In the table by maximum relationship, only the most related occurrence for each SOC and PT for each subject will be included in the summary.

Any adverse events that are not treatment emergent (occurred prior to the infusion) will be listed.

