### **8.4.1.3 Serious Adverse Events and Death**

Incidence and frequency of treatment emergent SAEs will be summarised for each of the IMP treated and HSCT control groups (data permitting) by system organ class (SOC) and preferred term (PT):

- overall,
- by maximum severity,
- by maximum relationship to treatment,
- treatment related SAEs.

In each table, if the same SOC or PT is reported on multiple occasions for a single subject, it will only be included once in the summary. In the table by maximum severity, only the most severe occurrence for each SOC and PT for each subject will be included in the summary. In the table by maximum relationship, only the most related occurrence for each SOC and PT for each subject will be included in the summary.

Any SAEs that are not treatment emergent (occurred prior to the infusion) will be listed.

If there are any deaths, the details will be listed.

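### Adverse events starting before the IMP infusion are listed but not counted, contrary to the protocol's by-phase safety analysis, and the treatment-emergent rule gives the HSCT controls no start point

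*SAP*

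**What the plan says.** SAP 8.4.1.1 counts an adverse event as treatment emergent "if it occurred on or after the date and time of the start of the IMP infusion". SAP 8.4.1.2 builds the AE summaries from treatment-emergent events, for the IMP-treated groups only, and adds: "Any adverse events that are not treatment emergent (occurred prior to the infusion) will be listed". SAP 8.4.1.3 does the same for serious events ("Any SAEs that are not treatment emergent (occurred prior to the infusion) will be listed") but extends those tables to the controls: "Incidence and frequency of treatment emergent SAEs will be summarised for each of the IMP treated and HSCT control groups", subject to the data being available.

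The protocol's Safety paragraph in 8.9.2 reads: "Safety will be analysed descriptively by arm and study phase using the safety analysis population". It adds that the safety data are to be analysed from before gene therapy until the study is completed, and leaves further detail to the SAP. Both documents carry the secondary objective "Evaluate tolerability of conditioning regimen" and assign its review and interpretation to the PI and study team (Protocol 4.2.2, SAP 4.2). In the visit schedule (Protocol Appendix 5, SAP 3), AE reporting begins in the Treatment column, which also holds harvest, conditioning and IMP administration.

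**The concern.** A child who receives this product also undergoes cell collection and busulfan. When cells are collected by leukapheresis, there is G-CSF mobilisation too, possibly with plerixafor. These steps come before infusion. Protocol 9.1.3 to 9.1.5 describes their risks, and 3.6 says the busulfan dosing differs from previous studies. Events that start during these steps are collected, but they receive no count or percentage in the tables that a reader of the report will use.

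The second problem is the control group. Protocol Appendix 8 states the aim of comparing safety as well as efficacy with HSCT, and the controls are in the safety population (SAP 7.2). The SAE tables are where that comparison would be made. If the start point for controls is left to the programmer, the two groups may be followed from different points in their treatment.

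**Working it through.** The plan states no figure to reproduce. The check is a timeline from the documents' own day numbers, followed by a comparison of the texts.

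**Length of the uncounted interval (infusion = day 0)**

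- Leukapheresis is on day -3 and marrow harvest on day -2 (Protocol 7.5.1).
- Leukapheresis takes place on G-CSF day 5 and/or 6 (Protocol 7.5.2).
- First G-CSF day = collection day − (G-CSF day of collection − 1). For day 5: −3 − 4 = day -7. For day 6: −3 − 5 = day -8. The interval is therefore about **7 to 8 days**.
- Marrow harvest without prior mobilisation: from day -2, so about **2 days**. Where marrow is used because mobilisation failed, the interval is longer by an amount the protocol does not fix.

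**Which conditioning events fall in the interval**

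- Busulfan starts after collection, during transduction, and at least 24 hours are left before infusion (Protocol 4.1, 7.5.6). Its start is therefore about day -3 to -2.
- Protocol Appendix 6 gives a median of 4 days to neutropenia in adults, without saying from when. From the start of busulfan: −3 + 4 = day +1, or −2 + 4 = day +2. From infusion it would be day +4.
- Acute reactions around dosing thus fall outside the tables, while typical cytopenia falls inside.

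**Effect on a table row**

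Each subject counts once per system organ class or preferred term (SAP 8.4.1.2). With 10 on-study subjects, one child is 1/10 = 10 percentage points. That is the most one affected child can move an on-study row, and only if the child has no post-infusion event under the same heading.

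**Protocol against SAP**

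- The protocol asks for analysis by study phase, beginning before gene therapy. The SAP has no phase breakdown and no table of pre-infusion events.
- For the tolerability objective, SAP 8.2.13 summarises whether conditioning was done, body size, busulfan dose and AUC. It contains no adverse events.
- Where the SAP leaves an item out because the study team will review it, it says so: the integration endpoints in 5.1 and transduction feasibility in 5.2. It makes no such statement for tolerability.

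**HSCT controls**

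A control with no IMP infusion can never meet the 8.4.1.1 condition. SAP 8.2.15 allows for controls who had gene therapy after their transplant. If that was this product, the rule would select only SAEs after the gene therapy. SAP 8.3.1.1 uses the date of transplant as the time origin for both groups, but this is not carried over to adverse events. Some control dates are missing and are replaced by ages in months. If these are whole months, the resolution is 365.25/12 = 30.4 days, too coarse to place an event before or after a transplant in the same month.

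**The case against.** The strongest reply is that starting at infusion is coherent: the IMP is the transduced cells, causality is assessed against the IMP (Protocol 11.2), and busulfan is a non-investigational product with its own reporting route (10.8). Nothing is hidden, because all pre-infusion events are listed, and with 10 on-study children plus the compassionate-use group a listing can be read in full. The protocol does not define study phase and defers detail to the SAP. Tolerability is assigned to the PI and study team. The partial-date rules lean towards inclusion, so an event with no start day in the month of infusion may be counted even if it began earlier. The HSCT gap touches only the SAE tables and is conditional on available data.

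Most of this stands, and it limits the size of the point. It also rules out three stronger inferences. A reader might conclude that busulfan toxicity as a whole drops out of the tables; the timeline does not support that, since only events with onset before infusion are left out. A reader might conclude that the plan conceals these events; the listings answer that. A reader might take each omitted event to lower an incidence by 10 points; the once-per-subject rule makes that a per-child maximum in the on-study column.

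The objection does not remove two things. A listing is not the descriptive analysis by phase that the protocol promises, and deferring detail to the SAP does not license dropping the breakdown. And the SAE tables for controls rest on a condition that controls without an IMP infusion cannot meet.

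**Conclusion.** The point holds in a limited form. AEs and SAEs with onset before infusion are collected and listed but, partial dates aside, not counted. This departs from Protocol 8.9.2 and leaves the conditioning-tolerability objective without a table of pre-infusion-onset events. The interval of about 7 to 8 days (leukapheresis) or 2 days (marrow) assumes the day numbering in Protocol 7.5.1 and G-CSF starting 4 to 5 days before collection. Placing most cytopenia after infusion relies on an adult median with no stated origin. How many events are affected cannot be known from the documents. Separately, the treatment-emergent rule cannot be applied as written to the HSCT controls. The SAP should be changed on both counts. The survival analyses are not affected, and the safety analyses remain descriptive.

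**What to change.** 1. Keep the post-infusion AE and SAE tables as planned.
2. For IMP-treated subjects, add AE and SAE tables by phase: mobilisation and harvest; start of conditioning to infusion; post-infusion. Name the middle phase, together with the post-infusion tables, as the material for the tolerability review.
3. For the SAE summary of IMP against HSCT, define one start in both groups: the date of transplant or infusion, as in SAP 8.3.1.1. Add a supplementary summary from the start of conditioning where dates permit, and state how unconditioned controls are handled. Mobilisation and harvest should stay out of this comparison, because counting autologous collection would add events to one group only.

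The cost is SAP wording, one derived phase variable and a few extra tables, with no new data for IMP-treated subjects. Counting pre-infusion events will make the reported safety profile slightly less favourable. The supplementary summary may be incomplete, because some control dates are missing.

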#### 8.4.1.2 Adverse Events

Treatment emergent adverse events will be summarised for each of the IMP treated groups in an overall summary presenting the number (%) of subjects with:

- any AE,
- moderate or severe AE,
- severe AE,
- treatment related AE (possibly/probably/definitely/not assessable/missing),
- AE leading to study withdrawal,
- any serious adverse event (SAE),
- treatment related SAE,
- SAE leading to death.

Incidence and frequency of treatment emergent AEs will be summarised for each of the IMP treated groups by system organ class (SOC) and preferred term (PT):

- overall,
- by maximum severity,
- by maximum relationship to treatment,
- treatment related AEs,
- AEs leading to study withdrawal (if sufficient events).

In addition, a summary table for the most frequently reported treatment emergent adverse events (those reported in 2 or more subjects) will be presented by PT in descending order of incidence and frequency.

In each table, if the same SOC or PT is reported on multiple occasions for a single subject, it will only be included once in the summary. In the table by maximum severity, only the most severe occurrence for each SOC and PT for each subject will be included in the summary. In the table by maximum relationship, only the most related occurrence for each SOC and PT for each subject will be included in the summary.

Any adverse events that are not treatment emergent (occurred prior to the infusion) will be listed.

### **8.4.1.3 Serious Adverse Events and Death**

Incidence and frequency of treatment emergent SAEs will be summarised for each of the IMP treated and HSCT control groups (data permitting) by system organ class (SOC) and preferred term (PT):

- overall,
- by maximum severity,
- by maximum relationship to treatment,
- treatment related SAEs.

In each table, if the same SOC or PT is reported on multiple occasions for a single subject, it will only be included once in the summary. In the table by maximum severity, only the most severe occurrence for each SOC and PT for each subject will be included in the summary. In the table by maximum relationship, only the most related occurrence for each SOC and PT for each subject will be included in the summary.

Any SAEs that are not treatment emergent (occurred prior to the infusion) will be listed.

If there are any deaths, the details will be listed.

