## Trial design and methods: Summary flowchart of the patients treated with gene therapy

**Recruitment period:** 5 years

**Trial duration per participant:** From consent until 3 years post-infusion of transduced CD34+ cells

**Estimated total trial duration:** 8 years

**Planned trial sites:** Great Ormond Street Hospital for Children NHS Foundation Trust (single-site trial)

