## Appendix 8: Details of the historical HSCT control group

### 1. Objective

Historical data from ADA-SCID patients who were treated with Hematopoietic Stem Cell Transplantation (HSCT) at GOSH during the period of 2000-2016 will be collected. HSCT is currently the standard of care for ADA-SCID patients. These data will be used as historical control group in a current on-going gene therapy study “Phase I/II, historical controlled, open-label, non-randomised, single-centre trial to assess the safety and efficacy of EF1αS-ADA lentiviral vector mediated gene modification of autologous CD34+ cells from ADA-deficient individuals”. The objective is to compare efficacy and safety of gene therapy versus HSCT to determine the optimal treatment.

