### 3. Data to be collected

GOSH holds a registry / clinical database (European Society for Immunodeficiencies (ESID) and European Society for Blood and Marrow Transplant (EBMT) Registry, GOSH BMT clinical database) displaying information on these types of patients. Patients treated with HSCT have been identified who received a transplant at GOSH between 2000-2016. . ESID and EBMT will allow us to collect the below information:

- Demographics (gender, date of birth, date of death if any),
- Method of ADA-SCID diagnosis,
- HSCT treatment(s) including: date of treatment, transplant cells, donor type and outcome

However, to make this historical control group valid for marketing authorisation application, our discussions with regulatory agencies suggests that we need to collect further information valuable to compare the efficacy and safety of any new treatment in research vs. current HSCT standard of care as:

- Previous PEG-ADA ERT (and duration of treatment),
- Previous or current immunoglobulin therapy,
- Listing of relevant medical history, including infections (severe or opportunistic infections)
- Vaccination history and immunological response to vaccination

- Auto-immune disease
- Malignant disease / leukaemia
- Graft versus host disease
- ADA activity and ADA metabolites
- AEs and SAEs

This information is only available from the patient's records; we therefore plan to re-consent these patients to access their full medical records.

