## 7 Analysis Populations

### 7.1 Efficacy Population

#### IMP Treated Subjects

The study protocol recruited 10 subjects with a diagnosis of ADA-SCID to be treated with IMP at GOSH. These subjects will be known as the “on-study” subjects.

In addition, a group of subjects were treated under a Compassionate Use Programme (CUP under GOSH Special License) either because the study was not yet open and urgent treatment was needed, because they were outside of the inclusion/exclusion criteria or because they followed a different process (i.e., received the IMP in two infusions). These subjects followed the same study schedule as the on-study subjects.

The primary efficacy population for analysis will consist of the on-study IMP treated subjects. A secondary efficacy population will consist of all IMP treated subjects (on-study and CUP)

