## **7.2 Safety Population**

The safety population will consist of all IMP treated subjects (on-study and CUP) and the complete HSCT historical control cohort consisting of ADA-SCID patients with any type of donor treated with HSCT at GOSH from the year 2000 onwards.

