## 8.2.16 Exposure

Duration of follow-up in months will be calculated for the IMP treated subjects as:

$$12 * (\text{date of final evaluation} - \text{date of infusion} + 1) / 365.25.$$

For the HSCT controls, the duration of follow-up will be recorded on the eCRF.

Duration of follow-up will be summarized for the IMP treated and the HSCT control groups using descriptive statistics. In addition, the total subject-years of follow-up in each treatment group will be presented.

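### SAE tables may set gene therapy (at most 3 years) beside HSCT controls with no stated follow-up cap, with no common time window, so equal risk can look like a safety advantage

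*SAP*

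**What the plan says.** The comparative SAE table is in SAP 8.4.1.3: "Incidence and frequency of treatment emergent SAEs will be summarised for each of the IMP treated and HSCT control groups". The same sentence makes the HSCT column conditional on data being available. The tables are by SOC and PT, and a subject with repeated reports of a term counts once. No window, truncation or person-time denominator is given.

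The two groups are observed for different lengths of time.

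- **Gene therapy.** The Protocol summary gives participation as "From consent until 3 years post-infusion of transduced CD34+ cells". For compassionate-use patients, SAP 7.1 says "These subjects followed the same study schedule as the on-study subjects", and the last visit on that schedule is at 36 months. The primary analysis (SAP 6) takes place once all on-study subjects have 12 months of follow-up.
- **HSCT controls.** SAP 7.2 takes "the complete HSCT historical control cohort consisting of ADA-SCID patients with any type of donor treated with HSCT at GOSH from the year 2000 onwards". Protocol Appendix 8 adds: "Patients treated with HSCT have been identified who received a transplant at GOSH between 2000-2016". On length of observation, SAP 8.2.16 says only: "For the HSCT controls, the duration of follow-up will be recorded on the eCRF".

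SAP 8.4.1.1 defines treatment emergence from the start of the IMP infusion and gives no equivalent start for controls. Appendix 8 states the purpose of the control data: "The objective is to compare efficacy and safety of gene therapy versus HSCT to determine the optimal treatment".

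**The concern.** The percentage of subjects who have ever had an event cannot fall as observation lengthens. If one column covers up to 3 years and the other covers whatever is on file for transplants since 2000, the columns measure different quantities, and a difference between them need not reflect a difference in risk. Reading the SAP's term frequency as a count of events does not help, because counts also grow with time.

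The SAP handles time elsewhere. Survival is read at 1, 2 and 3 years. Severe infections (8.3.2.3) are given as rates over follow-up time, with separate rates for the first 12 months and for the second and third years. The SAE tables have no such provision, and changing the infection section would leave them as they are.

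Within the SAP's safety section (8.4), this is the only place where gene therapy and HSCT stand side by side. A reader with the Appendix 8 objective in mind will use it to judge relative safety.

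**Working it through.** The documents give no SAE rate and no control follow-up time, so there is no planned figure to reproduce. The hazards and control follow-up times below are assumptions. The gene therapy ceiling of 3 years and the control period of 2000-2016 come from the documents.

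**1. Same constant hazard h in both groups.** P(event by T) = 1 - exp(-hT), for a single term.

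| h per year | 3 years | 8 years | 10 years | Gap, 8 vs 3 |
|---|---|---|---|---|
| 0.02 | 5.8% | 14.8% | 18.1% | 9.0 points |
| 0.05 | 13.9% | 33.0% | 39.3% | 19.0 points |
| 0.10 | 25.9% | 55.1% | 63.2% | 29.1 points |

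For h = 0.05: 1 - exp(-0.15) = 0.139, 1 - exp(-0.40) = 0.330, 1 - exp(-0.50) = 0.393. At 12 months, the shortest gene therapy follow-up at the primary analysis, the figure is 1 - exp(-0.05) = 4.9%. If controls had only 5 years, the figure would be 22.1%, a gap of 8.2 points over 3 years.

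**2. Plausibility of 8 to 10 years.** Spread transplants evenly over 2000-2016 and assume a data cut at the SAP date (10 January 2018). Potential follow-up then runs from 1.0 to 18.0 years with mean 9.5, and 88% exceed 3 years. This ignores deaths and is not a documented figure. At h = 0.05 the control column would read 36.0%, against 13.9% for gene therapy.

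**3. Front-loaded risk.** P = 1 - exp(-(h1 + h2(T - 1))), with h1 in year 1 and h2 afterwards.

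- h1 = 0.3, h2 = 0.02: 28.8% at 3 years, 35.6% at 8 years, gap 6.8 points.
- h1 = 1.0, h2 = 0.05: 66.7% and 74.1%, gap 7.4 points.
- h2 = 0: no gap.

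**4. Forces in the other direction.**

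- *Early deaths.* Protocol 3.2.1 reports 43% survival after haploidentical HSCT in a multicentre series, with most deaths after unrelated or haploidentical transplants inside 100 days. Suppose 57% of controls (100 - 43) leave observation at 0.27 years and the rest follow step 2. At h = 0.10, where step 2 gives 56.6%, non-fatal events reach 0.57 x (1 - exp(-0.027)) + 0.43 x 0.566 = 25.9%, equal to gene therapy. With 34% lost (matched unrelated donors, 66% survival) the figure is 38.3%. With 71% lost (mismatched unrelated donors, 29% survival) it is 18.3%, below gene therapy.
- *Under-recording.* If a fraction m of control SAEs is missing from the records, the columns agree when 8(1 - m) = 3, so m = 0.625. For 5 years m = 0.40, and for 10 years m = 0.70.

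**5. Effect of a common window.** With both groups cut at 36 months under step 2 and h = 0.05, the columns read 13.9% and 13.4%. The remaining difference comes from controls transplanted less than 3 years before the assumed cut.

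**6. Why one overall rate is not enough.** With h1 = 1.0 and h2 = 0.05, expected events per patient-year are (1.0 + 2 x 0.05)/3 = 0.37 over 3 years and (1.0 + 7 x 0.05)/8 = 0.17 over 8 years. A rate over all follow-up would then favour HSCT, so rates must be taken within windows.

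**The case against.** Several points on the other side stand.

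- The HSCT column appears only if data permit, and Appendix 8 says the records need fresh consent. The tables may be sparse or absent.
- Safety is declared descriptive (Protocol 8.9.2), and no test rests on these tables. The data analysis part of Appendix 8 lists survival, event-free survival, immunoglobulin use and infections, not SAEs.
- SAP 8.2.16 presents follow-up and total subject-years for each group, so a careful reader can see the imbalance. That does not correct a percentage for an individual SOC or PT.

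Three stronger readings are tempting, and the documents do not support them.

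- A reader might infer that these are the plan's only safety comparison with HSCT. They are the only one in section 8.4. Death is compared at fixed times and by Kaplan-Meier (8.3.1.1, 8.3.2.1), and infections that are opportunistic or involve hospitalisation are compared by rate and period (8.3.2.3). Both are filed under efficacy.
- A reader might infer that an any-SAE percentage will be set side by side. The explicit row of that kind (8.4.1.2) is for the IMP groups only. Section 8.4.1.3 promises SOC and PT tables.
- A reader might infer that gene therapy will certainly look safer. That needs controls who are in fact followed longer and SAEs that continue past the gene therapy window. Neither is documented, and the offsets in step 4 of the working can cancel or reverse the gap.

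What survives is that the table as specified has no common time basis.

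**Conclusion.** The concern holds in conditional form. Where controls are followed longer and SAEs continue beyond the gene therapy window, the tables can show a safety advantage for gene therapy when risk is equal. At an assumed 0.05 per year for one term, the gap at 3 years is 19 points against 8 years of control follow-up and about 25 points against 10 years (39.3 - 13.9 = 25.4). It is about 7 points in the front-loaded examples and zero if all SAEs occur early. These sizes rest on assumed hazards and assumed control follow-up.

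The direction in favour of gene therapy is likely but not certain. Early HSCT deaths and incomplete retrospective records push the other way. They do not make the crude table interpretable; they are further reasons to fix the window and show person-time. The lack of a stated start of emergence for controls is part of the same gap.

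**What to change.** Amend SAP 8.4.1.3, with a matching line in 8.4.1.1, for every SAE table that shows IMP beside HSCT:

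1. For controls, define emergence from the date of transplant, or from age at transplant where dates are not recorded.
2. Count only SAEs with onset in the same window after infusion or transplant: 0-12 months at the primary analysis, and 0-24 and 0-36 months at the later analyses.
3. Add events per patient-year within each window, extending the approach of 8.3.2.3.
4. Put later HSCT SAEs in a separate listing.

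The cost is a few SAP sentences, a start rule for controls and a date filter in programming. There are two downsides. Late HSCT events leave the comparative table, and control SAEs with neither an onset date nor an onset age can only be listed. The SAP already uses age in months for transplant, death or end of follow-up, and stopping of immunoglobulin and PEG-ADA. It does not say that age at SAE onset is captured, so check the control eCRF before the rule is finalised. Under-recording in the charts is a separate limitation that this change does not remove and that should be stated beside the tables.
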